
 
To determine the safety of dociparstat when added to best supportive care for the treatment of severe COVID-19
 
	
 
Incidence of AEs: overall, treatment-related, Grade 3 or higher in severity, serious, fatal, and those resulting in treatment discontinuation
 
Change from baseline in clinical laboratory parameters
 
Distribution of graded clinical laboratory results
 

Exploratory	

 
To determine the effect of dociparstat on viral load and biomarkers related to the pathophysiology of severe COVID-19
 
	
 
Change from baseline in levels of HMGB1, IL-6, TNF<math>\alpha</math>, SAA, and other biomarkers of inflammation
 
Change from baseline in SARS-CoV-2 viral load (Cohort 3 and Phase 3 only)
 

 
To evaluate the systemic exposure of dociparstat
 
	
 
Dociparstat plasma concentrations and PK parameters as data permit
 

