In the Phase 2 study of dociparstat for COPD (which was administered to 69 participants as an 8 mg/kg bolus followed by 0.375 mg/kg/hr over 96 hours), there were very few instances of minor/moderate bleeding. During continuous IV infusion of dociparstat, the aPTT was prolonged in all the participants with a mean of  $\leq 8$  seconds from baseline, determined daily. This does not seem to impose added risks for bleeding in this population, in accordance with the findings in healthy volunteers from the 3 Phase I studies with dociparstat; as discussed above, these effects could in fact ameliorate the disseminated intravascular coagulopathy that seems to characterize severe cases of COVID-19. The dociparstat effect on ALT (observed in 37% of dociparstat recipients vs. 11% of placebo recipients in the COPD study) is a class effect to all heparins, heparin derivatives, LMWHs, and heparinoids; this occurs on approximately Day 5 or 7 of exposure with return to baseline values by Day 14 after treatment discontinuation. A total of 50 SAEs were reported during the double-blind portion of the study; of these, 27 SAEs were reported in the placebo group by 14 participants and 23 SAEs reported in the dociparstat group by 17 participants. Eight deaths occurred during the study; 5 in the placebo group and 3 in the

dociparstat group, none of them were considered as related to study intervention by the investigators.

This Phase 2/3 study of dociparstat in participants with severe COVID-19 lung disease seeks to determine whether there is evidence that dociparstat can prevent or mitigate respiratory failure and the need for ventilator support. Dociparstat given as a bolus of 4 mg/kg followed by a continuous infusion for up to 7 days was also generally well tolerated when administered with systemic chemotherapy (anthracycline plus cytarabine for AML, and gemcitabine plus nab-paclitaxel for pancreatic cancer).

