#### **9.4.3.2. Laboratory Results**

Descriptive statistics (N, mean, SD, median, Q1, Q3, minimum, and maximum) will be provided for each continuous laboratory test as follows:

- Baseline values
- Values at each postbaseline analysis window (to be defined in the SAP)
- Change from baseline at each postbaseline analysis window

The minimum, maximum, and last postbaseline value / change from baseline will also be summarized. Missing data will not be imputed.

Laboratory tests will be descriptively analyzed by grade and analysis window using counts and percentages. The maximum and last postbaseline grade for each participant will also be summarized. Denominators will be the number of participants with a graded (or normal) test during the window. Laboratory tests with criteria for both increased and decreased levels will be analyzed for each direction (i.e., increased and decreased). This analysis will be generated twice to count (1) treatment-emergent increases in laboratory grades (i.e., only those above the baseline grade) and (2) any grade regardless of baseline.

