Aspartate Aminotransferase (AST)	>ULN - 3.0 x ULN	>3.0 - 5.0 x ULN	>5.0 - 20.0 x ULN	>20.0 x ULN
Alanine Aminotransferase (ALT)	>ULN - 3.0 x ULN	>3.0 - 5.0 x ULN	>5.0 - 20.0 x ULN	>20.0 x ULN
Total Bilirubin	>ULN - 1.5 x ULN	>1.5 - 3.0 x ULN	>3.0 - 10.0 x ULN	>10.0 x ULN
Creatinine	>ULN - 1.5 x ULN	>1.5 - 3.0 x ULN	>3.0 - 6.0 x ULN	>6.0 x ULN
Creatinine Clearance, Estimated	<LLN - 60 ml/min	<60 - 30 ml/min	<30 - 15 ml/min	<15 ml/min

NA = Not applicable, ULN = Upper limit of normal, LLN = Lower limit of normal.

Grade 0 : Any result not graded 1, 2, 3, 4 or Unknown.

Grade Unknown : Missing result or missing upper limit of normal for parameters requiring ULN for grading.

(Notes for programmer:

- LLN for creatinine clearance is fixed 90 mL/min
- Calculation of creatinine clearance (CC) (Cockcroft-Gault):

$$(140 - \text{age (years)})$$

$$CC \text{ (ml/min)} = \frac{140 - \text{age (years)}}{0.8143 \times \text{serum creatinine (}\mu\text{mol/L)}} \times \text{baseline weight (kg)} \times (0.85 \text{ if female})$$

)

Table 14: Distribution of laboratory grade by parameter and visit - Safety Set

Parameter: <Hemoglobin> <Platelets> <Activated partial thromboplastin time (aPTT)> <Prothrombin International Normalized Ratio (INR)> <Aspartate aminotransferase (AST)> <Alanine aminotransferase (ALT)> <Total bilirubin> <Creatinine> <Creatinine Clearance, Estimated >

Scheduled Visit Grades (a)	DSTAT 0.25 N=xxx	Cohort 1 PBO N=xxx	DSTAT 0.325 N=xxx	Cohort 2 PBO N=xxx
Baseline				
Grade 0	xx (xx.x)	xx (xx.x)	xx (xx.x)	xx (xx.x)
Grade 1	xx (xx.x)	xx (xx.x)	xx (xx.x)	xx (xx.x)
Grade 2	xx (xx.x)	xx (xx.x)	xx (xx.x)	xx (xx.x)
Grade 3	xx (xx.x)	xx (xx.x)	xx (xx.x)	xx (xx.x)
Grade 4	xx (xx.x)	xx (xx.x)	xx (xx.x)	xx (xx.x)
Unknown	xx (xx.x)	xx (xx.x)	xx (xx.x)	xx (xx.x)
Maximum Post-baseline Grade				
Grade 0	xx (xx.x)	xx (xx.x)	xx (xx.x)	xx (xx.x)
Grade 1	xx (xx.x)	xx (xx.x)	xx (xx.x)	xx (xx.x)
Grade 2	xx (xx.x)	xx (xx.x)	xx (xx.x)	xx (xx.x)
Grade 3	xx (xx.x)	xx (xx.x)	xx (xx.x)	xx (xx.x)
Grade 4	xx (xx.x)	xx (xx.x)	xx (xx.x)	xx (xx.x)
Unknown	xx (xx.x)	xx (xx.x)	xx (xx.x)	xx (xx.x)

N = Number of subjects in a specific group; n = Number of subjects with data available; Percentages are based on N; (a) CTCAE v5.0 grades using absolute thresholds without accounting for baseline.

Baseline value is defined as the last non-missing measurement prior to, or on the date/time of the first administration of study treatment.

NA = not applicable

Page X of Y

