(Notes for programmer:

- CTCAE Grades: Unknown: missing result (or missing upper limit of normal for parameters requiring ULN for grading). Grade 0: any result not graded 1, 2, 3, 4 or Unknown.
- display only for visit Baseline and Maximum Grade per subject and all 6 categories (Grade 0 - Grade 4 and Unknown), if applicable.
- generate a post-baseline Maximum Grade per subject (incl. unscheduled measurements)
- for the generation of Maximum Grade use the following order: Unknown - Grade 0 - Grade 1, ..., Grade 4)
- Calculation of creatinine clearance (CC) (Cockcroft-Gault):
(140 - age (years))

CC (ml/min) = ----- * baseline weight (kg) * (0.85 if female)
0.8143 * serum creatinine (μmol/L)

)

Table 15: Listing of laboratory results - Safety Set

Subject Age/Sex/Race	Treatment Group	Parameter	Date/Time	Visit	Value \$	Unit	Lower Limit	Upper Limit	Grade (a)	
999-999 70/F/W	DSTAT 0.25	Hemoglobin	Ddmmmyy/mm:hh	Screening	99999 H	NCS	Unit	LLL	UUU	1
			Ddmmmyy/mm:hh	Baseline	99999 L	CS	Unit	LLL	UUU	4

(a) CTCAE v5.0 grades using absolute thresholds without accounting for baseline. Grade=0 and Grade=Unknown are not displayed.
\$: H = Above upper limit of normal; L = Below lower limit of normal, NCS = Not clinically significant, CS= Clinically significant.
Visit "Early Tx DC (TXDC)" denotes Early Treatment Discontinuation Visit.

(Notes for programmer:

- Sorted by subject number, Parameter, date and time
- The following parameter will be displayed: Hemoglobin, platelets, activated partial thromboplastin time (aPTT), prothrombin time (PT), prothrombin international normal ratio (INR), d-dimer, Anti-Xa, aspartate aminotransferase (AST), alanine aminotransferase (ALT), total bilirubin, creatinine, Creatinine Clearance, Estimated.
- LLN for creatinine clearance is fixed 90 mL/min
- CTCAE Grades: reference Table 13.)

Table 16: Shift-table of laboratory results - Safety Set

Parameter: <Hemoglobin> <Platelets> <Activated partial thromboplastin time (aPTT)> <prothrombin time (PT)> <Prothrombin International Normalized Ratio (INR)> <d-dimer> <Anti-Xa> <Aspartate aminotransferase (AST)> <Alanine aminotransferase (ALT)> <Total bilirubin> <Creatinine> <Creatinine Clearance, Estimated>

DSTAT 0.25 N=xxx				Cohort 1 PBO N=xxx				Baseline (D1)				DSTAT 0.325 N=xxx				Cohort 2 PBO N=xxx																										
<LLN			Normal	>ULN			<LLN			Normal	>ULN			<LLN			Normal	>ULN			<LLN			Normal	>ULN																	
Post-Baseline																																										

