Minimum, n (%)																																										
<LLN																																										
Normal																																										
>ULN																																										
Post-Baseline																																										
Maximum, n (%)																																										
<LLN																																										
Normal																																										
>ULN																																										

N = Number of subjects in a specific group; n = Number of subjects with data available; Percentages are based on N;

Normal: Within normal range, LLN: Lower limit of normal, ULN: Upper limit of normal.

Only subjects with baseline and at least one post-baseline value are considered.

Baseline value is defined as the last non-missing measurement prior to, or on the date/time of the first administration of study treatment. NA = not applicable.

Page X of Y

(Notes for programmer:

- generate a post-baseline Maximum Value and post-baseline Minimum Value per subject (incl. unscheduled measurements
- LLN for creatinine clearance is fixed 90 mL/min
- if ULN (eg CC) available, please display n/a
-)

Figure 3: Selected laboratory parameters over time (Box-Whisker-Plot) - Safety Set

Box-Whisker-Plots: by <Parameter> (<unit>), Cohort X, Reference Ranges xxx - yyyy <unit>

y-axis:

range: depending on data
label: Value

x-axis:

range: Visits : Screening, D1 to D28 (depending on data) visit. Incl Early Tx DC at the end of the x-axis.

label: Visit

Box-Whisker Plots:

different styles/colors for the treatment-groups

Plots shifted to not overlap

Default SAS Box-Whisker-Plots - Min, 25%, Median, 75%, Max. Whiskers as 1.5 IQR. Mean included.

Footnotes to be used for the Box-Whisker-Plots :

Visit "Early Tx DC (TXDC)" denotes Early Treatment Discontinuation Visit. Reference Ranges do not necessarily present "values of concern" in this population but will give some context to the results relative to a normal population.

(Notes for programmer:

- replace <Parameter> <unit>, in label by actual parameter and unit used
- Adapt Visits as relevant for the different parameters. Not all parameters are reported for all visits, only scheduled visits to be included in the Figure

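### SAP 5.1 gives no summary of change from baseline in laboratory values and no count of grades above the baseline grade, although protocol 9.4.3.2 specifies both

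*SAP*

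**What the plan says.** **Protocol.** Section 3 lists "Change from baseline in clinical laboratory parameters" as a safety endpoint, on a separate line from the distribution of graded results. Section 9.4.3.2 asks for N, mean, SD, median, quartiles and range of three things for each continuous test: the baseline value, the value in each window, and "Change from baseline at each postbaseline analysis window". It also asks for the minimum, maximum and last post-baseline value and change. The grade analysis is to be run twice. One run ignores baseline; the other counts "treatment-emergent increases in laboratory grades (i.e., only those above the baseline grade".

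**SAP 5.1.** The laboratory outputs are:
- Table 13: the grade definitions.
- Table 14: grade distributions at baseline and at the post-baseline maximum, footnoted as "CTCAE v5.0 grades using absolute thresholds without accounting for baseline".
- "Table 15: Listing of laboratory results - Safety Set": each participant's values by date and visit, with limits and grade.
- "Table 16: Shift-table of laboratory results - Safety Set": baseline category (below, within or above normal) against the categories of the post-baseline minimum and maximum.
- Figure 3: box plots of raw values for 12 parameters, specified as "Default SAS Box-Whisker-Plots - Min, 25%, Median, 75%, Max. Whiskers as 1.5 IQR. Mean included", restricted to scheduled visits.

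For laboratory data, SAP 5.2 adds only line plots of central-laboratory biomarkers.

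**The concern.** Protocol 2.3.1 singles out prolonged aPTT and raised hepatic enzymes as risks of particular interest. On the earlier COPD study, Section 4.3 says: "During continuous IV infusion of dociparstat, the aPTT was prolonged in all the participants with a mean of" at most 8 s from baseline. It also reports an ALT effect in 37% of dociparstat recipients against 11% on placebo. These are continuous shifts, and the natural summary is each participant's change from their own baseline.

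Many participants may start above normal. The exclusion criteria admit aPTT up to 42 s and ALT up to 5x ULN, and heparin or enoxaparin prophylaxis is permitted. Grades and normal-range categories are least sensitive in exactly those participants.

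The outputs also have a use. SAP Section 2 says the first part of the analysis is equivalent to the DMC output for Cohort 2, and protocol 9.6 has the DMC review Cohorts 1 and 2 before recommending the Cohort 3 dose.

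**Working it through.** **Step 1. Required against provided.**

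| Protocol 9.4.3.2 | SAP 5.1 |
|---|---|
| Descriptive statistics of baseline and of value per window | No numeric table; box plots only (Figure 3) |
| Descriptive statistics of change per window | None |
| Minimum, maximum and last value and change | Minimum and maximum by normal-range category only (Table 16) |
| Grades regardless of baseline | Table 14 |
| Grades above the baseline grade | None |

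**Step 2. aPTT.** Inputs: Grade 1 is above ULN up to 1.5 x ULN (SAP Table 13); the interruption rule begins at aPTT above 50 s (protocol 7.1); the entry limit is 42 s. Local ULNs are not given. I assume 35 s, the upper end of the range that the SAP uses for box-plot reference lines.
- Grade 1 ceiling: 1.5 x 35 = 52.5 s. Band width: 52.5 - 35 = 17.5 s.
- 36 to 44 s (+8), 42 to 50 s (+8) and 38 to 52 s (+14) all stay Grade 1 in Table 14 and above normal in Table 16. The last passes 50 s.
- The highest baseline that stays Grade 1 after +8 s is 52.5 - 8 = 44.5 s, which is above the 42 s entry limit. So an 8 s rise from any above-normal baseline within the entry limit changes no cell in either table.
- The 50 s threshold lies inside Grade 1 when 1.5 x ULN is at least 50, that is, when ULN is at least 50/1.5 = 33.3 s. At 33 s the band ends at 49.5 s and the threshold falls in Grade 2. At 40 s it ends at 60 s.

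**Step 3. ALT.** Inputs: Grade 1 is above ULN up to 3.0 x ULN (SAP Table 13). Assumed ULN is 40 U/L, again from the box-plot reference range.
- Grade 1 ceiling: 3 x 40 = 120 U/L, so a rise of up to 80 U/L (nearly threefold) can stay within it.
- 45 to 115 U/L (115/45 = 2.6-fold) changes no cell in either table.
- 50 to 130 U/L crosses into Grade 2. Table 14 then shows a higher maximum grade; Table 16 still reads above normal to above normal.

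**Step 4. What Table 14 cannot link.** Baseline and maximum grades appear as two separate distributions. Suppose one participant goes from Grade 1 to Grade 2 and another from Grade 2 to Grade 1. The two distributions are identical, and both participants stay above normal in Table 16. A count of grades above baseline would show the rise.

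**The case against.** The strongest reply has four parts.

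- **Continuous data are in the package.** Figure 3 gives quartiles, median, mean and extremes by visit and treatment group, and Table 15 lists every value. With 12 participants per cohort, a reviewer can read individual changes from the listing. This stands. One might infer that the SAP reports laboratory data only in categories, or that raised values vanish; the documents do not support that. Figure 3, however, shows unpaired raw values and leaves out unscheduled repeats, and Table 15 leaves the subtraction to the reader.
- **Large rises surface elsewhere.** Rises that cross a grade limit generally raise the maximum in Table 14, and an aPTT excursion that leads to interruption appears in Table 4. This also stands. The blind spot in Tables 14 and 16 is mainly the within-band rise, plus the missing link to the participant's own baseline.
- **The 35 s limit is not the grading limit.** Correct. The SAP proposes it for plots because ranges differ by center, so 52.5 s is illustrative. The 33.3 s condition in Step 2 does not depend on it.
- **This SAP covers only the post-Cohort 1/2 lock, and a Phase 2 SAP is due before the Cohort 3 analysis.** So one cannot say that the endpoint has been dropped from the study. Deferral does not close the gap, though. The output is labelled final and unblinded, it uses data through end of study, and its Section 5.1 matches the Cohort 2 DMC package. A summary that first appears with the Cohort 3 analysis comes after the Cohort 3 dose is chosen. Protocol 9.4 limits Cohorts 1 and 2 to descriptive analyses, but the missing summaries are descriptive.

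It is also tempting to express the loss as statistical power. The documents give no SD for change in aPTT, and protocol 9.4.3 generally plans no inference on safety endpoints, so I attach no power figure.

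**Conclusion.** The point holds as a gap between protocol and SAP: one named safety endpoint has no summary output, and one of the two specified grade analyses is missing. That conclusion comes from comparing the texts and needs no assumption.

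The consequence is limited but real. Under ULNs of 35 s and 40 U/L, aPTT rises of up to 17.5 s and ALT rises of up to 80 U/L from just above normal are invisible in both summary tables. For aPTT the hidden band includes the 50 s threshold at any local ULN of about 33.3 s or more.

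The documents do not show that the dose review was misled, since the raw values were available to it in plots and listings. Nor do they show that the later SAPs omit these summaries. This should be fixed, but it does not touch the efficacy analyses.

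**What to change.** Add two outputs to SAP 5.1:

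1. The table that protocol 9.4.3.2 describes. By cohort and arm, give N, mean, SD, median, Q1, Q3, minimum and maximum of baseline, value and change from baseline at each scheduled visit. Add the minimum, maximum and last post-baseline value and change, with unscheduled values included.
2. Next to Table 14, a cross-tabulation of baseline grade by maximum post-baseline grade, or a count of participants whose grade rises above baseline.

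Keep Tables 14 to 16 and Figure 3. A ratio to baseline for ALT and AST would be a useful option, but the protocol's laboratory analysis does not ask for it.

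The cost is one or two table programs on data already collected, SAP wording, and a slightly longer output package. No protocol amendment is needed.

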5.2. ADDITIONAL POST-COHORT 2 LOCK ANALYSES – TABLE SHELLS

Figure 4: Biomarkers during the course of the study – Safety Set

Line-plots

Biomarker: <HMGB1 (SI-unit)> <IL-6 (SI-unit)> <TNF alpha (SI-unit)> <SAA (SI-unit)> – see list of Biomarkers on the next page

y-axis:

range: depending on data
label: Value (unit)

x-axis:

range: Baseline (D1), Day 3 (D3), Day 5 (D5), Day 7 (D7), Day 14 (D14), Day 28 (D28)
label: Visit
Line-Plots: different line styles/colors to differentiate cohort/group

Lines:

one line per subject
4 different line styles/colors to differentiate cohort/group

(Notes for programmer:

- one figure per biomarker,
- additional Biomarkers might be added on short notice of sponsor
- "(SI-unit) » in sub-title to be replaced by actual SI-unit
-)

See list of Biomarkers provided by Chimerix on 9Dec2020

25964	SAA,EDTApl(-70)RUO387PNL	ng/mL	ng/mL	Biomarkers
25965	IL-6,EDTApl(-70)RUO387PNL	pg/mL	pg/mL	Biomarkers
25966	TNF-alpha,EDTApl(-70)RUO387PNL	pg/mL	pg/mL	Biomarkers
26776	AT-III,EDTApl(-80)RUO387	ug/mL	ug/mL	Biomarkers
26777	Ficolin-3,EDTApl(-80)RUO387	ug/mL	ug/mL	Biomarkers
5592	GM-CSF, EDTApl(-80)RUO-387	pg/mL	pg/mL	Biomarkers
5593	IFN-gamma,EDTApl(-80)RUO-387	pg/mL	pg/mL	Biomarkers
5594	IL-10, EDTApl(-80)RUO-387	pg/mL	pg/mL	Biomarkers
5615	IL-18, EDTApl(-80)RUO-387	pg/mL	pg/mL	Biomarkers
5597	IL-2, EDTApl(-80)RUO-387	pg/mL	pg/mL	Biomarkers
5632	IL-3, EDTApl(-80)RUO-387	ng/mL	ng/mL	Biomarkers
5627	IL-4, EDTApl(-80)RUO-387	pg/mL	pg/mL	Biomarkers
5598	IL-5, EDTApl(-80)RUO-387	pg/mL	pg/mL	Biomarkers
5617	IL-7, EDTApl(-80)RUO-387	pg/mL	pg/mL	Biomarkers
5600	IL-8, EDTApl(-80)RUO-387	pg/mL	pg/mL	Biomarkers
26778	LRG1,EDTApl(-80)RUO387	ug/mL	ug/mL	Biomarkers
5623	MIP1 alpha, EDTApl(-80)RUO-387	pg/mL	pg/mL	Biomarkers
5624	MIP-1b, EDTApl(-80)RUO-387	pg/mL	pg/mL	Biomarkers
5619	MCP-1, EDTApl(-80)RUO-387	pg/mL	pg/mL	Biomarkers
26779	Nr-CAM,EDTApl(-80)RUO387	ng/mL	ng/mL	Biomarkers
26780	Neuropilin-1,EDTApl(-80)RUO387	ng/mL	ng/mL	Biomarkers
26781	NAP-2,EDTApl(-80)RUO387	ng/mL	ng/mL	Biomarkers
26782	PEDF,EDTApl(-80)RUO387	ng/mL	ng/mL	Biomarkers
26783	RAGE,EDTApl(-80)RUO387	ng/mL	ng/mL	Biomarkers
26784	SHBG,EDTApl(-80)RUO387	nmol/L	nmol/L	Biomarkers
26785	Sortilin,EDTApl(-80)RUO387	ng/mL	ng/mL	Biomarkers
26786	SOD-1,EDTApl(-80)RUO387	ng/mL	ng/mL	Biomarkers
26787	TA阜,EDTApl(-80)RUO387	ug/mL	ug/mL	Biomarkers
5626	TNF beta, EDTApl(-80)RUO-387	pg/mL	pg/mL	Biomarkers
8966	HMGB1,K3EDTApl(-70)RUO639	pg/mL	pg/mL	Biomarkers

Table 18: Proportion of and time to invasive mechanical ventilation or all-cause mortality - ITT Set

	DSTAT 0.25 N=xxx	Cohort 1 PBO N=xxx	DSTAT 0.325 N=xxx	Cohort 2 PBO N=xxx
Number of subjects who are alive and free of invasive mechanical ventilation or ECMO through Day 28 (a)	xx (xx.x)	xx (xx.x)	xx (xx.x)	xx (xx.x)
Number of subjects with any invasive mechanical ventilation, ECMO, all-cause mortality or early study discontinuation, whatever comes first, n (%) (b)	xx (xx.x)	xx (xx.x)	xx (xx.x)	xx (xx.x)
Any invasive mechanical ventilation, ECMO	xx (xx.x)	xx (xx.x)	xx (xx.x)	xx (xx.x)
Death	xx (xx.x)	xx (xx.x)	xx (xx.x)	xx (xx.x)
Early study discontinuation < Day 25	xx (xx.x)	xx (xx.x)	xx (xx.x)	xx (xx.x)
Kaplan-Meier estimates (c)				
Number of censored subjects, n (%) (c)	xx (xx.x)	xx (xx.x)	xx (xx.x)	xx (xx.x)
Time to first invasive mechanical ventilation, ECMO or all-cause mortality (days) (c)				
25% Quartile (95% CI)	x.x (x.xx,x.xx)	x.x (x.xx,x.xx)	x.x (x.xx,x.xx)	x.x (x.xx,x.xx)
Median (95% CI)	x.x (x.xx,x.xx)	x.x (x.xx,x.xx)	x.x (x.xx,x.xx)	x.x (x.xx,x.xx)
75% Quartile (95% CI)	x.x (x.xx,x.xx)	x.x (x.xx,x.xx)	x.x (x.xx,x.xx)	x.x (x.xx,x.xx)

N = Number of subjects in a specific group; n = Number of subjects with data available; Percentages are based on N; ECMO: Extracorporeal membrane oxygenation.

(a) Early study discontinuation before Day 25 are not included.

(b) Subjects with any invasive mechanical ventilation, ECMO, all-cause mortality or early study discontinuation before Day 25 will be counted as event.

(c) Kaplan-Meier estimates: Subjects with any invasive mechanical ventilation, ECMO or all-cause mortality will be counted as event. All other subjects will be censored. Time to first invasive mechanical ventilation, ECMO or all-cause mortality, whatever comes first (days): Days are calculated as (start date/time - first study drug date/time)/24h). Time will be censored at last individual date/time reported. If time is not available for events "00:01" will be imputed, for censored observations "23:59" will be imputed. Randomized untreated subjects will be censored at time = 0.

Page X of Y

(Notes for programmer: Subjects randomized not treated will be counted in

- a) as failure, and therefore not included in (a)
- b) as event (in the line "Early study discontinuation < Day 25") in case of early study discontinuation < Day 25
- c) as censored observation (censor time = 0)

)

Figure 5: Time to invasive mechanical ventilation, ECMO or all-cause mortality (KM-Plot) - ITT Set

Kaplan-Meier Plot:

y-axis:

range: 0% to 100% by 20%
label: Event-free Probability
reference-line: 50%

x-axis:

range: 0 to xxx (depending on data), by 7 days
label: Time to Event (Days)

Lines:

solid
different colors/line styles for the treatment-groups
starting at (100%/Baseline)
Censored values marked

Footnote:

N = Number of subjects in a specific group; (+) = censored values;

Kaplan-Meier estimates: Subjects with any invasive mechanical ventilation, ECMO or all-cause mortality will be counted as event.
All other subjects will be censored.

Time to first invasive mechanical ventilation, ECMO or all-cause mortality, whatever comes first (days): Days are calculated as
(start date/time - first study drug date/time)/24h). Time will be censored at last individual date/time reported. If time is not
available for events "00:01" will be imputed, for censored observations "23:59" will be imputed. Randomized untreated subjects will
be censored at time = 0.

(Notes for programmer: Subjects randomized not treated will be counted as censored observation (censor time = 0)

)

Table 19: Proportion of and time to all-cause mortality - ITT Set

	DSTAT 0.25 N=xxx	Cohort 1 PBO N=xxx	DSTAT 0.325 N=xxx	Cohort 2 PBO N=xxx
Number of subjects with all-cause mortality or early study discontinuation, n (%) (a)	xx (xx.x)	xx (xx.x)	xx (xx.x)	xx (xx.x)
Death	xx (xx.x)	xx (xx.x)	xx (xx.x)	xx (xx.x)
Early study discontinuation < Day 25	xx (xx.x)	xx (xx.x)	xx (xx.x)	xx (xx.x)
Kaplan-Meier estimates (b)				
Number of censored subjects, n (%) (b)	xx (xx.x)	xx (xx.x)	xx (xx.x)	xx (xx.x)
Time to all-cause mortality (days) (b)				
25% Quartile (95% CI)	x.x (x.xx,x.xx)	x.x (x.xx,x.xx)	x.x (x.xx,x.xx)	x.x (x.xx,x.xx)
Median (95% CI)	x.x (x.xx,x.xx)	x.x (x.xx,x.xx)	x.x (x.xx,x.xx)	x.x (x.xx,x.xx)
75% Quartile (95% CI)	x.x (x.xx,x.xx)	x.x (x.xx,x.xx)	x.x (x.xx,x.xx)	x.x (x.xx,x.xx)

N = Number of subjects in a specific group; n = Number of subjects with data available; Percentages are based on N;
 (a) Subjects with all-cause mortality or early study discontinuation before Day 25 will be counted as event.

(b) Kaplan-Meier estimates: Subjects who died will be counted as events. All other subjects will be censored. Time to all-cause mortality (days): Days are calculated as (start date/time - first study drug date/time)/24h). Time will be censored at last individual date/time reported. If time is not available for events "00:01" will be imputed, for censored observations "23:59" will be imputed. Randomized untreated subjects will be censored at time = 0.

Page X of Y

(Notes for programmer: Subjects randomized not treated will be counted in

- a) as event (in the line "Early study discontinuation < Day 25") in case of early study discontinuation < Day 25
- b) as censored observation (censor time = 0)

)

Figure 6: Time to all-cause mortality (KM-Plot) - ITT Set

Kaplan-Meier Plot:

y-axis:

range: 0% to 100% by 20%
label: Event-free Probability
reference-line: 50%

x-axis:

range: 0 to xxx (depending on data), by 7 days
label: Time to Event (Days)

Lines:

solid
different colors/line styles for the treatment-groups
starting at (100%/Baseline)
Censored values marked

Footnote:

N = Number of subjects in a specific group; (+) = censored values;

Kaplan-Meier estimates: Subjects who died will be counted as event. All other subjects will be censored.

Time to all-cause mortality (days): Days are calculated as (start date/time - first study drug date/time)/24h). Time will be censored at last individual date/time reported. If time is not available for events "00:01" will be imputed, for censored observations "23:59" will be imputed. Randomized untreated subjects will be censored at time = 0.

*(Notes for programmer: Subjects randomized not treated will be counted as censored observation (censor time = 0)
)*

Table 20: Proportion of participants who are alive, discharged from the hospital, and not using home oxygen - ITT Set

Visit	DSTAT 0.25 N=xxx n (%)	Cohort 1 PBO N=xxx n (%)	DSTAT 0.325 N=xxx n (%)	Cohort 2 PBO N=xxx n (%)
Day 8 (D8)	xx (xx.x)	xx (xx.x)	xx (xx.x)	xx (xx.x)
Day 14 (D14)	xx (xx.x)	xx (xx.x)	xx (xx.x)	xx (xx.x)
Day 28 (D28)	xx (xx.x)	xx (xx.x)	xx (xx.x)	xx (xx.x)

N = Number of subjects in a specific group; n = Number of subjects with data available;

Subjects who discontinued study early prior to start of time window (-3 days to -1 day for each visit) will be considered as failures even if alive and last records indicate no oxygen and out of hospital.

If the discontinuation is within the time window for the respective visit the last available status to be considered.

Page X of Y

(Notes for programmer:

Number of subjects who are alive, discharged from the hospital and not using home oxygen are defined based on the Ventilator/Oxygen/Medical Care Status and the Hospitalization/Activity Status eCRF pages:

All subjects who are

- not hospitalized (either with limited activities or not) AND
- do not require oxygen (no matter whether ongoing medical care is required or not)

at the specific time points will meet this endpoint.

Use the CDISC study day - for corresponding start and stop date (e.g. hospitalization stop date, or start date of not require oxygen) and assign the relevant study days to the corresponding visit (Day 8, Day 14 and Day 28).

- Determine status on particular day with respect to death, hospitalization, and oxygen use. For example, if a subject starts oxygen (e.g. Nasal Supplemental Oxygen) on Day -1 and stops on Day 10, subject is using oxygen at Visit Day 8, subject is not using oxygen at Day 14 and Day 28.
- If can't determine one, pick the **worst status** on that day. For example oxygen stops on Day 8, subject will be considered to be on oxygen for Day 8 analysis and subject is not using oxygen at Day 14 and Day 28. Subject discharge from the hospital on Day 8, subject will be considered to be in the hospital for Day 8 analysis and to be discharged from the hospital on Day 14 and Day 28.
- Subjects who discontinued study early **PRIOR** to start of time window (-3 days to -1 day for each visit) will be failures even if alive and last records indicate no oxygen and out of hospital. Subjects who discontinued study early but within the time window of the respective visit, e.g. on Day 7, discharged from hospital earlier and not using home oxygen will be considered with the last available status at Day 8 (= no failure), and as failure at Day 14 and Day 28. Subjects who discontinued study early on Day 10 will be considered as failure at Day 14 and Day 28.)
- Subjects randomized not treated will be counted as failure at the respective visit in case of early study discontinuation prior to start of the time window (-3 days to -1 day for each visit).

Table 21: Clinical status assessed by the NIAID ordinal scale at fixed time points - ITT Set

Visit NIAID Score	DSTAT 0.25 N=xxx n (%)	Cohort 1 PBO N=xxx n (%)	DSTAT 0.325 N=xxx n (%)	Cohort 2 PBO N=xxx n (%)
Day 8 (D8)				
1	xx (xx.x)	xx (xx.x)	xx (xx.x)	xx (xx.x)
2	xx (xx.x)	xx (xx.x)	xx (xx.x)	xx (xx.x)
3	xx (xx.x)	xx (xx.x)	xx (xx.x)	xx (xx.x)
4	xx (xx.x)	xx (xx.x)	xx (xx.x)	xx (xx.x)
5	xx (xx.x)	xx (xx.x)	xx (xx.x)	xx (xx.x)
6	xx (xx.x)	xx (xx.x)	xx (xx.x)	xx (xx.x)
7	xx (xx.x)	xx (xx.x)	xx (xx.x)	xx (xx.x)
8	xx (xx.x)	xx (xx.x)	xx (xx.x)	xx (xx.x)
Missing	xx (xx.x)	xx (xx.x)	xx (xx.x)	xx (xx.x)
Day 14 (D14)				
1	xx (xx.x)	xx (xx.x)	xx (xx.x)	xx (xx.x)
2	xx (xx.x)	xx (xx.x)	xx (xx.x)	xx (xx.x)
3	xx (xx.x)	xx (xx.x)	xx (xx.x)	xx (xx.x)
4	xx (xx.x)	xx (xx.x)	xx (xx.x)	xx (xx.x)
5	xx (xx.x)	xx (xx.x)	xx (xx.x)	xx (xx.x)
6	xx (xx.x)	xx (xx.x)	xx (xx.x)	xx (xx.x)
7	xx (xx.x)	xx (xx.x)	xx (xx.x)	xx (xx.x)
8	xx (xx.x)	xx (xx.x)	xx (xx.x)	xx (xx.x)
Missing	xx (xx.x)	xx (xx.x)	xx (xx.x)	xx (xx.x)
Day 28 (D28)				
1	xx (xx.x)	xx (xx.x)	xx (xx.x)	xx (xx.x)
2	xx (xx.x)	xx (xx.x)	xx (xx.x)	xx (xx.x)
3	xx (xx.x)	xx (xx.x)	xx (xx.x)	xx (xx.x)
4	xx (xx.x)	xx (xx.x)	xx (xx.x)	xx (xx.x)
5	xx (xx.x)	xx (xx.x)	xx (xx.x)	xx (xx.x)
6	xx (xx.x)	xx (xx.x)	xx (xx.x)	xx (xx.x)
7	xx (xx.x)	xx (xx.x)	xx (xx.x)	xx (xx.x)
8	xx (xx.x)	xx (xx.x)	xx (xx.x)	xx (xx.x)
Missing	xx (xx.x)	xx (xx.x)	xx (xx.x)	xx (xx.x)

N = Number of subjects in a specific group; n = Number of subjects with data available; Percentages are based on N;
 NIAID scores are derived according to Appendix 4 of the study protocol. Higher values indicates a better outcome.
 For subjects who discontinued study early within the time window (-3 days to - 1 day for each visit), the last available NIAID scale will be used at the corresponding visit and a NIAID score = missing to be assigned to all visits after early study discontinuation date.

Page X of Y

(Notes for programmer:

This document is confidential.

Page 38 of 45

Use a skeleton and include all 8 NIAID scores in the table for each visit and include Missing category)

The NIAID ordinal score at the predefined time points will be derived based on the eCRF data collected on the Ventilator/Oxygen/Medical Care Status, the Hospitalizations/Activities Status pages and the death date. In the event subjects transition from one score to another on a particular Day, the worse score will be used.

Use the CDISC study day - for corresponding start and stop date (e.g. hospitalization stop date, or start date of nasal supplemental oxygen) and assign the relevant study days to the corresponding visit (Day 8, Day 14 and Day 28).

- Determine status on particular day with respect to death, hospitalization, and ventilatory care status. For example, if a subject starts nasal supplemental oxygen on Day -1 and stops on Day 10, and if the subject is still in hospital at Day 8, a NIAID score = 4 to be assigned at Day 8.
- If can't determine one, pick the worst status on that day.
For example nasal supplemental oxygen stops on Day 8, and subject does not require oxygen but requires ongoing medical care starting on Day 8, and the subject is in hospital at Visit Day 8, a NIAID score = 4 to be assigned at Day 8.
- For subjects who discontinued study early within the time window (-3 days to -1 day for each visit), the last available NIAID score will be used at the corresponding visit and a NIAID score = missing will be assigned to all visits after early study discontinuation date.
E.g. if a subject withdraws from study on Day 7, his or her last NIAID score will be assigned to Day 8, and NIAID scores at Day 14 and Day 28 are considered as missing. If subject withdrawal on Day 8, his or her Day 8 NIAID score will be assigned to Day 8, and NIAID scores at Day 14 and Day 28 are considered as missing.
- For subjects who died e.g. prior to or on Day 8 a NIAID score = 1 will be assigned for the visits on and after Day 8
- Subjects randomized not treated will be counted as missing at the respective visit in case of early study discontinuation prior to start of the time window (-3 days to -1 day for each visit).
)

Table 22: Time to clinical improvement - ITT Set

	DSTAT 0.25 N=xxx	Cohort 1 PBO N=xxx	DSTAT 0.325 N=xxx	Cohort 2 PBO N=xxx
Number of participants with clinical improvement, n (%) (a)	xx (xx.x)	xx (xx.x)	xx (xx.x)	xx (xx.x)
Kaplan-Meier estimates (b)				
Number of censored subjects, n (%) (b)	xx (xx.x)	xx (xx.x)	xx (xx.x)	xx (xx.x)
Number of subjects without improvement	xx (xx.x)	xx (xx.x)	xx (xx.x)	xx (xx.x)
Death	xx (xx.x)	xx (xx.x)	xx (xx.x)	xx (xx.x)
Time to clinical improvement (days) (b)				
25% Quartile (95% CI)	x.x (x.xx,x.xx)	x.x (x.xx,x.xx)	x.x (x.xx,x.xx)	x.x (x.xx,x.xx)
Median (95% CI)	x.x (x.xx,x.xx)	x.x (x.xx,x.xx)	x.x (x.xx,x.xx)	x.x (x.xx,x.xx)
75% Quartile (95% CI)	x.x (x.xx,x.xx)	x.x (x.xx,x.xx)	x.x (x.xx,x.xx)	x.x (x.xx,x.xx)

N = Number of subjects in a specific group; n = Number of subjects with data available; Percentages are based on N; Clinical improvement is defined as at least a 2-grade improvement from baseline on the NIAID ordinal score.

(a) Subjects with a clinical improvement will be counted as event.

(b) Kaplan-Meier estimates: Subjects with a clinical improvement will be counted as event. Subjects without a clinical improvement or deaths occurring prior to the positive event will be censored. Time to clinical improvement: Days are calculated as (start date/time - first study drug date/time)/24h. Time will be censored at last individual date/time reported. If time is not available for events "23:59" will be imputed, for censored observations "00:01" will be imputed. Participants who died prior to Day 28 without clinical improvement will be censored at Day 28. Randomized untreated subjects will be censored at time = 0.

Page X of Y

(Notes for programmer: Subjects randomized not treated will be counted as censored observation (censor time = 0)
)

Figure 7: Time to clinical improvement (KM-Plot) - ITT Set

Kaplan-Meier Plot:

y-axis:

range: 0% to 100% by 20%
label: Event Probability
reference-line: 50%

x-axis:

range: 0 to xxx (depending on data), by 7 days
label: Time to Event (Days)

Lines:

solid
different colors/line styles for the treatment-groups
starting at (0%/Baseline)
Censored values marked

Footnote:

N = Number of subjects in a specific group; (+) = censored values;

Clinical improvement is defined as at least a 2-grade improvement from baseline on the NIAID ordinal score.

Kaplan-Meier estimates: Subjects with a clinical improvement will be counted as event. Subjects without a clinical improvement or deaths occurring prior to the positive event will be censored.

Time to clinical improvement (days): Days are calculated as (start date/time - first study drug date/time)/24h). Time will be censored at last individual date/time reported. If time is not available for events "23:59" will be imputed, for censored observations "00:01" will be imputed. Participants who died prior to Day 28 without clinical improvement will be censored at Day 28. Randomized untreated subjects will be censored at time = 0.

(Notes for programmer: Subjects randomized not treated will be counted as censored observation (censor time = 0)

)

Table 23: Number of ventilator-free days from baseline through Day 28 - ITT Set

	DSTAT 0.25 N=xxx	Cohort 1 PBO N=xxx	DSTAT 0.325 N=xxx	Cohort 2 PBO N=xxx
Number of ventilator-free days, n(%)				
0	xx (xx.x)	xx (xx.x)	xx (xx.x)	xx (xx.x)
1	xx (xx.x)	xx (xx.x)	xx (xx.x)	xx (xx.x)
2	xx (xx.x)	xx (xx.x)	xx (xx.x)	xx (xx.x)
3	xx (xx.x)	xx (xx.x)	xx (xx.x)	xx (xx.x)
